**Mulligan Concept Intervention for Pregnancy Related Lumbo-
Pelvic Pain**

NCT number: TBD

Research Strategy

February 7, 2018

Research Strategy

Significance

Pregnancy-related pelvic girdle pain (PPGP), whether of the pelvic girdle or the lumbopelvic junction, is exceptionally prevalent; reportedly, 45-76% of all pregnant women and 25% of postpartum women suffer from PPGP.³⁻⁸ A major cause of sick leave during pregnancy,¹⁷ PPGP greatly affects activities of daily living and is associated with risk of long-term back pain.^{7, 9-10} Women suffering from PPGP typically seek treatment from their primary care physician or obstetrician. Primary care physicians have historically been more responsible for providing pregnancy related care in the Pacific and Inland Northwest regions compared to national averages; however, a marked decline in the provision of pregnancy related care has occurred in Alaska, Idaho, Montana, and Wyoming since 1999.^{1, 11}

Maternal health disparities exist in rural communities and are accompanied by poor health outcomes and increased healthcare costs.¹¹ Consequently, a call has been made for solutions stemming from problems related to diminishing access to care.^{1,3} Limited access means that positive and impactful patient outcomes at each visit are even more critical. Giving health care professionals more effective intervention options can help make limited visits more efficient, increase patient outcomes, decrease maternal health disparity in rural communities, as well as help women across the nation.

Researchers and clinicians have theorized PPGP to be caused by a widening of the pelvis in response to hormonal changes during pregnancy, creating instability in the sacroiliac (SI) joints.^{3, 12} While the theory is logical, evidence does not support hormone induced ligament laxity having a role in the etiology of PPGP.⁶ A more likely cause is mechanical dysfunction, such as malposition of bones in the lumbopelvic region, which has been observed in radiographic and gait analysis studies.^{3, 5, 12, 15} Mechanical changes are correlated with failure of the load transfer mechanism of the SI joints, movement dysfunction, and pain.¹⁴ Clinical intervention for PPGP ranges from acupuncture to stabilization exercises to corticosteroid injections, with only mildly positive results because these treatments are not aimed at correcting underlying mechanical and motor control dysfunction.¹⁰

The Mulligan Concept is a manual therapy paradigm used to correct pain of mechanical origin by using specific joint mobilizations with limb movement to restore functional relationships between joint surfaces. The purported benefits of the Mulligan Concept are an immediate reduction or abolition of pain, immediate restoration of function, and options for self-treatment.^{15, 14, 16} The effects of a manual therapy intervention aimed at restoring mechanical and motor control function of the lumbopelvic region have yet to be measured in women with PPGP. The proposed project will improve knowledge surrounding PPGP and create evidence for clinical practice options. If the proposed aims are achieved, we will have a better understanding of the efficacy of the Mulligan Concept for use in the pregnant population, build upon current research associating poor motor control to PPGP, and introduce novel assessment and treatment procedures for women suffering from PPGP.

Innovation

There is growing consensus that the etiology of PPGP is not due to hormonally induced laxity, but a combination of mechanical and motor control dysfunctions.^{3, 5, 8, 12} Researchers have identified gait characteristics and joint relationships differences that are unique to patients with PPGP; not found in pregnant women with out PPGP or in patients with simple low back pain.^{3, 8, 10} Positional abnormalities (e.g., subluxation of the pubic symphysis), changes in gait (e.g., thoracic and lumbar rotation timing and amplitude), and muscle activation patterns have been associated with the syndrome but

not found in matched healthy subjects.^{3, 8,13} Failure of the load transfer mechanism of the sacroiliac joints, specifically, is associated with positional displacements of the joints in pelvic girdle and can cause dysfunctional pelvic girdle movement, loss of motor control, pain and disability.¹⁸⁻²⁰ Researchers have yet to conduct intervention trials to determine whether these associated dysfunctions can be altered with treatment. A clinician utilizing the Mulligan Concept would aim to simultaneously restore the load transfer mechanism and correct the malpositioning of the joints of the pelvis through mobilizations and patient movement. The concept is novel and has yet to be tested in this population. This application seeks to shift current research toward clinical intervention trials that close the evidence-based medicine gap and aim to inform clinical practice.

Approach

Twenty pregnant volunteers, ages 20-45 years, will be recruited for the study. Participants will be between their 20th-34th week of gestation, with reported pregnancy-related lumbopelvic pain. Participants would be excluded for any of the following criteria:

- orthopaedic or neurological problems with walking (other than PPGP)
- prior surgery of the lumbar spine, pelvis, hip, or knee
- fracture
- known malignancy
- active inflammation in the lumbar spine or pelvis
- ankylosing spondylitis, Scheuermann's kyphosis, active polyarthritis, or severe osteoporosis
- any pulmonary, cardiac, visual, auditory, or cognitive disorders
- any other multi/co-morbidities that limit the volunteers ability to complete a gait and sit-to-stand task

Volunteers will be recruited from Latah County, Idaho and surrounding areas by word of mouth and print and social media. Pregnant women who express interest in the study will be given an informational packet explaining the methods, risks, and benefits of participation. If the women decide to participate they would sign a consent statement and conduct an initial questionnaire, sent via online link. The survey would be used to determine inclusion and exclusion criteria, and group assignment (i.e., intervention group, placebo group). Un-paired t-tests will be conducted to determine whether significant differences exist between intervention and control groups in age, weight, height, as well as gestational week and number of pregnancies. Randomly stratifying the participants in to groups in this manner minimizes the potential confounding variables.

Participants will report to the University of Idaho Integrated Sport Medicine and Rehabilitative Therapy Clinic for initial patient reported outcome measures collection and standardized examination. Primary patient reported outcome measures include the Visual Analog Pain Scale, the Pelvic Girdle Questionnaire, the Assessment of Disablement Questionnaire, the Patient Specific Function Scale, and the Short Stress State Questionnaire. The examination will include history, palpation, special tests (e.g., Posterior Pelvic Pain Provocation test, Active Straight Leg Raise), and neurological screen.

Each participant will then perform a walking gait and sit-to-stand task as a baseline, in the University of Idaho Biomechanics Laboratory. An eight-infrared camera optical system (Vicon Motion Systems Ltd., Oxford, UK) and forceplate (AMTI, Watertown, MA, USA) will be used to collect the kinematic and kinetics data during the tasks. In addition, an eight-channel wireless electromyography (EMG) system (Delays, Inc., Natick, MA, USA) will be used to collect muscle activity during the gait and sit-to-

stand tasks, and the active straight leg raise (ASLR) special test. The participants in the treatment group will receive a Mulligan Concept evaluation and treatment administered by a Certified Mulligan Practitioner. The placebo group will undergo only the Mulligan Concept evaluation. The same tasks and ASLR will be repeated. Outcome measures and physical examination will also be repeated.

The study will be conducted under a randomized triple blinded placebo trial design. Neither the participants, the treating clinician, biomechanist, nor researcher collecting outcome measures will know the group designation of the participants. Conducting the trial in this manner will ensure the lowest possibility that any observed effects of the intervention are due to confounding factors.

Statistical Analysis

Sample size calculations were conducted to determine the appropriate number of participants that must be included. A sample size of 17 participants per group is needed to detect differences between groups with 80% power, and an *a priori* alpha of 0.05. Accounting for a reasonable 5% drop out rate, the final recommended number of participants is 36 (18 participants per group).

Specific Aim #1: Determine if Mulligan Concept manual therapy produces immediate changes in pain and self-reported function in women with PPGP.

A series of independent samples t-tests will be used to determine if a difference exists between the mean scores of the intervention and placebo groups on the VAS, PSFS, ADQ, and PGQ.

Specific Aim #2: Determine whether treatment with the Mulligan Concept immediately restores or alters dysfunctional gait characteristics and pelvic girdle motor control in women experiencing PPGP.

The timing and amplitude of lumbar and thoracic spine rotations, as well as muscle activity, will be recorded and compared using descriptive statistics. Between groups analysis will consist of descriptive statistics to compare differences in timing, amplitude, and EMG activity after intervention.

Specific Aim #3: Identify intake factors that predict treatment outcome.

Standard multiple regression and step-wise multiple regression will be used to predict treatment outcome from different factors of interest (e.g., number of pregnancies, week of gestation, initial ADQ score, etc.).

Project Timeline

Preparation for participant recruitment will begin July 15th, 2017. Participant recruitment will take place between December 2017 and March 2018. Data collection will take place over 5-6 days in late March 2018. Data Analysis will take place between April and May 2018. Abstract and manuscript development and preparation for publication and presentation will take place through December 2018.

Interim Milestones

The following interim milestones will be used to hold the PI and research team accountable. These milestones will be shared with the research team and overseen by the PI. When appropriate and if a milestone is not met in a timely fashion, guidance will be sought from the Mentor and a plan for re-establishing the project timeline will be established and implemented.

Phase	Milestone	Timeline
Study Start Up	
 • IRB Approval • Award Announcement • Preparation • Pre-recruitment planning (e.g., creation of media material) 	
 • Prior to March 1, 2017 • May 31, 2017 • July 15- October 1, 2017 • October 1- December 1, 2017
Study Conduct	
 • Ready to Recruit • Materials completely distributed • 50% Enrollment Achieved • 100% Enrollment Achieved • Data Collection 	
 • December 1, 2017 • January 15, 2018 • February 20, 2018 • March 15, 2018 • Late March, 2018
Study Close-out	
 • Attendance at Annual Meeting • Publication within 12 months of study close 	
 • May, 2018 • December, 2018

Plans for developing and submitting future grant applications

This grant application marks continued steps toward becoming an independent and successful researcher. The project will enable the PI to further establish her work in patient-care and manual therapy research, where she has had previous experience in relation to core motor control. Additionally, this project will aid in the PI's professional development by establishing University and community collaborations.

Information gathered from this exploratory trial will greatly inform next steps in a long line of research and allows the PI to collect preliminary data and develop evidence for interventions in an underserved population. For example, if the central hypothesis is confirmed, further investigation into the Mulligan Concept as treatment for PPGP in this population is warranted. A larger-scale multi-site randomized control trial with large sample size and more diverse sample would be the next logical step to create more robust evidence of the technique. Once the efficacy of the treatment protocol is established, exploration of a patient-applied treatment as a home program would be developed. If the kinematic, kinetic, pain and dysfunction effects can be well established, continued research would not necessarily focus on the biomechanical mechanisms, but would be more clinical in nature; a full scale clinical trial, focusing on treatment outcome, comorbidity, predictive factors of treatment outcome, risks, and side effects, etc. Future research will not be equipment heavy, but need funding primarily for participant recruitment, clinician training, and researcher salaries. Exploratory/Developmental research grants such as the NIH R21, or multi-site collaborative grants such as the CTR-IN Multi-Site Research Project Program, would be an ideal funding mechanisms for the next stages of this research line.

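### The Approach recruits 20 women, but the power statement needs 17 per group (36 enrolled); the plan does not say which number governs

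*Combined protocol and SAP*

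**What the plan says.** The Approach section opens with the recruitment target: "Twenty pregnant volunteers, ages 20-45 years, will be recruited for the study". It gives no split between the groups and does not refer to a sample size calculation.

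The Statistical Analysis section then gives a different number. It introduces its calculation in binding terms, "Sample size calculations were conducted to determine the appropriate number of participants that must be included", and reports the result: "A sample size of 17 participants per group is needed to detect differences between groups with 80% power", at an alpha of 0.05. After an allowance of 5% for dropout, it states that "the final recommended number of participants is 36 (18 participants per group". It does not give the effect size, the SD, the sidedness of the test or the outcome on which the calculation was based.

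Two other places might have settled the matter but do not. The Interim Milestones table sets dates for 50% and 100% enrolment without a denominator. The section on future grant applications calls the study exploratory ("Information gathered from this exploratory trial will greatly inform next steps in a long line of research") but does not use this to justify a smaller sample.

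**The concern.** Enrolment is a basic design quantity, and here it has two values. Twenty is below both the 34 evaluable participants the calculation calls for (2 × 17) and the 36 to be enrolled. Reading twenty as a per-group figure does not help: that would be 40 in total, and the sentence refers to the whole study.

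A reader therefore cannot tell how many women will be enrolled, or whether the 80% power claim applies to this trial. The milestones inherit the ambiguity, since half of enrolment is either 10 or 18 women. If 20 is the operative number, a non-significant result under Specific Aim 1 would be read against a power claim the design does not meet. If 36 is operative, the recruitment text understates enrolment by 16.

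**Working it through.** **Inputs from the document.** Approach: 20 in total. Statistical Analysis: 17 per group, 80% power, alpha 0.05, 5% dropout, 18 per group enrolled. The test for Aim 1 comes from the same section: "A series of independent samples t-tests will be used".

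**Inputs the document does not give, and what is assumed.**
- Allocation of the 20: 1:1, so 10 per group.
- Sidedness: two-sided is the natural reading, because the tests "will be used to determine if a difference exists between the mean scores of the intervention and placebo groups". One-sided is shown as a variant.
- Effect size d (difference in SD units): back-solved from the plan's own n.
- One unadjusted test.

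**Step 1: reproduce the plan's figure.** Enrolled = evaluable / (1 − dropout) = 34 / 0.95 = 35.8, rounded up to 36. Per group, 17 / 0.95 = 17.9, rounded up to 18. The dropout step is correct. The 17 itself cannot be checked without an effect size.

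**Step 2: the gap.** 36 − 20 = 16 participants, and 16 / 36 = 44% fewer than the enrolment figure. Against the 34 evaluable it is 34 − 20 = 14, and 14 / 34 = 41%. This step needs no assumption.

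**Step 3: the effect implied by 17 per group.** Power of the two-sample t-test comes from the noncentral t distribution with df = n1 + n2 − 2 and noncentrality d × √(n1·n2 / (n1 + n2)). Because n is rounded up, the implied d lies between the value with exactly 80% power at 17 per group and the value with exactly 80% power at 16 per group.
- Two-sided: d = 0.991 to 1.024.
- One-sided: d = 0.871 to 0.900.

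**Step 4: power at the smaller sample.** Five per cent dropout from 20 leaves 20 × 0.95 = 19, that is 10 vs 9. For example, two-sided at 10 vs 10 with d = 0.991, the noncentrality is 0.991 × √5 = 2.216 on 18 df, which gives power 0.555.

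| Evaluable | Two-sided (d 0.991 to 1.024) | One-sided (d 0.871 to 0.900) |
|---|---|---|
| 17 vs 17 | 80% to 82% | 80% to 82% |
| 10 vs 10 | 55% to 58% | 59% to 61% |
| 10 vs 9 | 53% to 56% | 57% to 59% |
| 9 vs 9 | 51% to 53% | 55% to 57% |

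The rows for 10 vs 10 and 10 vs 9 together span 53% to 61%. The chance of missing the implied effect is then 100 − 61 = 39% to 100 − 53 = 47%, against the planned 20%.

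**Step 5: detectable difference at 80% power.** With 10 per group it is 1.32 SD two-sided, against 0.99 with 17 per group (1.325 / 0.991 = 1.34). One-sided it is 1.16 SD against 0.87 (1.156 / 0.871 = 1.33). Either way it is about one third larger.

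**The case against.** The strongest reply has three parts.

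First, the power loss is not documented. It rests on an effect size inferred from the plan's n, and it arises only if 20 is the operative number; if 36 is, there is no loss. This is right. The documented defect is 20 against 36, and the power figures illustrate one branch of it.

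Second, the 53-61% range is a choice. Its upper part needs a one-sided test, which the wording of Aim 1 does not suggest; the same two-sided cases give 53-58%. Its lower end allows one loss in total, whereas the plan's own inflation allows one per group (18 to 17). The parallel case, 9 vs 9, gives 51% two-sided. A one-sided normal approximation at 10 per group gives up to 63%. These points stand, but they move the limits by about two points and do not change the conclusion. The best single figure is about 55%: two-sided, no dropout, at the effect for which 17 per group gives exactly 80%.

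Third, the study is described as exploratory and leaves firmer evidence to a larger multi-site trial, so low power matters less. An exploratory trial may well be small. But the document does not make that argument for 20, and a small exploratory trial should not carry an 80% power statement for a sample it will not recruit.

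**Conclusion.** The concern holds and must be fixed. The plan contains two incompatible enrolment numbers, and that conclusion rests on no assumption. The arithmetic inside the sample size paragraph is sound; the fault is the conflict between sections. The size of the consequence depends on which number governs:

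- **If 36 governs:** the 80% claim is unaffected and only the recruitment sentence is wrong.
- **If 20 governs:** the stated power overstates what the trial can deliver by roughly 25 percentage points (80 − 55) at the back-solved two-sided effect. This figure is conditional on 1:1 allocation, a single unadjusted t-test and that inferred effect. At any effect for which 17 per group is genuinely needed, 10 per group falls well short of 80%.

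**What to change.** State one enrolment number in both the Approach and the Statistical Analysis sections, and put that number beside the percentages in the Interim Milestones table.

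**If 36 is the plan,** correct the number in the Approach. The text change is one word, but it commits the team to 16 more women than that section plans. The document is dated 7 February 2018 and the milestone for full enrolment is 15 March 2018, so about five weeks remained. The Project Timeline says "Data collection will take place over 5-6 days in late March 2018". Assuming one session per participant, the load rises from 3.3-4.0 a day (20 / 6 to 20 / 5) to 6.0-7.2 a day (36 / 6 to 36 / 5), and the team should confirm that this is feasible.

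**If 20 is the plan,** replace the 80% power sentence with the power and detectable difference for 10 per group, computed from the sponsor's own planning effect, SD and sidedness, and state those inputs. About 55% power, and 1.32 SD for 80% power, serve as check values under the back-solved two-sided effect; they are not proposed protocol text. The cost is wording only, and a less favourable power statement. If the exploratory purpose is the reason for the smaller sample, the plan should say so there.

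The planned t-tests can stay as they are in either case.

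### Aim 1 does not adjust for the baseline scores the trial already collects, and the five baseline t-tests are no substitute for adjustment

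*Combined protocol and SAP*

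**What the plan says.** In the Approach section of the combined protocol and SAP, the plan says that "Un-paired t-tests will be conducted to determine whether significant differences exist between intervention and control groups in age, weight, height". The same sentence adds two further variables: the week of gestation and how many pregnancies the participant has had. That makes five variables. The next sentence reads "Randomly stratifying the participants in to groups in this manner minimizes the potential confounding variables". No stratification factor or randomisation method is defined, and the plan does not say what would follow a significant baseline result.

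The VAS, PGQ, ADQ and PSFS are collected at the clinic visit before treatment and repeated afterwards. None of them is among the five variables compared at baseline.

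Under Statistical Analysis, Specific Aim #1, the plan says "A series of independent samples t-tests will be used to determine if a difference exists between the mean scores" of the two groups on those four scales. It names no covariate, and it does not say whether the scores are post-treatment values or changes from baseline. An initial score (the ADQ) is named as a model term only under Specific Aim #3, as a possible predictor of outcome.

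The planned size appears twice. Approach says "Twenty pregnant volunteers, ages 20-45 years, will be recruited for the study". Statistical Analysis says "A sample size of 17 participants per group is needed to detect differences between groups with 80% power", raised to 18 per group (36 in total) for 5% dropout.

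**The concern.** Two things stand out together. The plan tests characteristics that are only loosely tied to the outcomes, and it leaves unused in the treatment comparison the baseline values most closely tied to them. It also follows the tests with a statement that confounding is minimised, which tests of this kind cannot support.

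The stake is mainly precision. In a trial this small, a chance difference in starting pain or function is common and carries through to an unadjusted comparison. The data needed to remove it are already being collected.

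**Working it through.** **Inputs from the documents.** Five baseline variables; 20 participants (Approach) or 18 per group (Statistical Analysis); alpha 0.05; 17 evaluable per group; 5% dropout.

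**Assumptions.** 1:1 allocation of the 20, so 10 per group; two-sided tests; true randomisation; approximately normal scores with equal SDs before and after treatment; baseline-post correlation r of 0.5 to 0.7. The documents give no correlation, SD or effect size.

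**The plan's own figure.** 17/0.95 = 17.9, rounded up to 18 per group and 36 in total. This reproduces. The 17 cannot be derived, because no effect size is given.

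**Chance of a false flag among the five tests.** If independent: 1 − 0.95^5 = 0.226. The tests are probably not independent (height and weight, for example). Whatever the dependence, the chance cannot exceed 5 × 0.05 = 0.25, and it would be 0.05 if the tests were fully dependent.

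**Largest observed difference still called non-significant**, in SD units: t(0.975, 2n − 2) × √(2/n).
- n = 10: 2.101 × 0.447 = 0.94 SD
- n = 18: 2.032 × 0.333 = 0.68 SD

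The tests are also weak as a check for faulty allocation. By the noncentral t distribution, power to flag a systematic difference of 0.5 SD is 18.5% at 10 per group and 30.8% at 18.

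**Chance of a gap of 0.5 SD or more on one given score**: P(|Z| > 0.5/√(2/n)).
- n = 10: P(|Z| > 1.118) = 0.264
- n = 18: P(|Z| > 1.5) = 0.134

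**What a 0.5 SD gap does to the unadjusted comparison.**
- Post-treatment scores: shift = r × 0.5, which is 0.25 SD at r = 0.5 and 0.35 SD at r = 0.7, in the direction of the gap.
- Change scores: shift = (r − 1) × 0.5, which is −0.25 SD and −0.15 SD, in the opposite direction.

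Given a gap of exactly 0.5 SD and no treatment effect, the post-score comparison is approximately normal with mean 0.5r and variance (1 − r²)(2/n). The chance that it exceeds 1.96 × √(2/n) in absolute value is 8.2% (r = 0.5) to 10.1% (r = 0.7) at 18 per group, and 5.5% to 5.0% at 10 per group.

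**Precision gained by ANCOVA.** The large-sample ratio of standard errors is √(1 − r²) against a post-score t-test and √((1 + r)/2) against a change-score t-test. Estimating the covariate slope inflates the expected ANCOVA variance by (N − 3)/(N − 4): 17/16 = 1.0625 at N = 20 and 33/32 = 1.031 at N = 36. The standard error therefore rises by a factor of 1.031 or 1.016.

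| Comparator | r | Large-sample ratio | Reduction, large sample | Reduction, N = 20 | Reduction, N = 36 |
|---|---|---|---|---|---|
| Post score | 0.5 | 0.866 | 13% | 11% | 12% |
| Post score | 0.7 | 0.714 | 29% | 26% | 27% |
| Change score | 0.5 | 0.866 | 13% | 11% | 12% |
| Change score | 0.7 | 0.922 | 8% | 5% | 6% |

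**The case against.** The strongest reply is that nothing here is invalid. Under true randomisation an unadjusted t-test is unbiased and keeps its 5% error rate. The 26% and 13% chance gaps are ordinary sampling variation that its standard error already covers, and the baseline tests as written change no Aim 1 estimate or p-value. This stands. Adjustment brings precision and removes the shift that is conditional on the observed imbalance; it does not repair a broken test.

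A second reply is that the plan never says non-significant tests prove comparability. The grammatical subject of the sentence on confounding is random stratification. The link to the t-tests rests on the words *in this manner*, which could also point to the survey-based assignment or to the allocation procedure as a whole. This also stands, so the criticism of that sentence is conditional on how it is read.

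A third is that Aim 1 is about immediate changes, so the mean scores may be change scores. The gain is then smaller, and a baseline gap pushes the estimate the other way. That is correct and is why both cases are shown. A change-score t-test still does not adjust fully for baseline, so the recommendation is unaffected.

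Finally, leaving pain and function scores out of the significance tests is not itself a fault, because such tests are better dropped. What matters is that the scores are absent from the Aim 1 model and from any stated comparison of the groups at baseline.

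**Conclusion.** The point holds as a near-free improvement in precision. Aim 1 names no baseline adjustment, and the only stated baseline check is uninformative under randomisation at either planned size. For r between 0.5 and 0.7, ANCOVA reduces the standard error by 13–29% against post-treatment scores or 8–13% against change scores in large samples. At 20 to 36 participants the ranges are 11–27% and 5–12%. These figures rest on the assumed correlation and on equal SDs before and after treatment; the figures for 10 per group also assume 1:1 allocation of the 20.

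A reader might infer three stronger things that the documents do not support:
- That the Aim 1 comparison is biased. The shift is conditional on the imbalance that happens to occur; over repeated randomisations it averages to zero.
- That the plan relies on non-significance to declare the groups comparable. That is one reading of an ambiguous sentence.
- That an imbalance in pain would go unseen, or that a significant test would lead to regrouping. The scores are collected and can be inspected, and no action after a significant result is described.

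**What to change.** - In Specific Aim #1, pre-specify an ANCOVA for each of VAS, PSFS, ADQ and PGQ: post-treatment score as the response, group as the factor, and that scale's own baseline score as covariate, plus any stratification factor actually used. This also settles whether post-treatment or change scores are analysed.
- In Approach, replace the five t-tests with a descriptive table by group (means and SDs, or medians and ranges) that includes the four baseline scores.
- State that covariates will not be chosen from baseline p-values.
- Reword the sentence on confounding so that it credits randomisation and not these tests, and name the stratification factors or remove the reference to stratifying.

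The cost is wording and one residual degree of freedom per covariate; no new data are needed. If the baseline tests were in fact meant to be part of the allocation procedure, that procedure would have to be rewritten too, and the change would go beyond the analysis text.

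### The control arm is labelled a placebo but receives only the evaluation common to both arms, so Aim 1 estimates the effect of adding treatment to evaluation and cannot credit the mobilization itself

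*Combined protocol and SAP*

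**What the plan says.** The arms are defined in two sentences of the Approach section. For the active arm: "The participants in the treatment group will receive a Mulligan Concept evaluation and treatment administered by a Certified Mulligan Practitioner". For the control arm: "The placebo group will undergo only the Mulligan Concept evaluation". The tasks, the outcome measures and the physical examination are then repeated in both arms.

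The next paragraph presents the study as a randomized, triple-blinded placebo trial. On blinding it says: "Neither the participants, the treating clinician, biomechanist, nor researcher collecting outcome measures will know the group designation of the participants". On what this achieves: "Conducting the trial in this manner will ensure the lowest possibility that any observed effects of the intervention are due to confounding factors".

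In the Statistical Analysis section, Specific Aim #1 is to "Determine if Mulligan Concept manual therapy produces immediate changes in pain and self-reported function in women with PPGP". The analysis is stated as: "A series of independent samples t-tests will be used to determine if a difference exists between the mean scores of the intervention and placebo groups", applied to four self-reported scores (VAS, PSFS, ADQ and PGQ). The Significance section describes the active ingredient as "using specific joint mobilizations with limb movement to restore functional relationships between joint surfaces" and says that meeting the aims would improve understanding of the method's efficacy in pregnant women.

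No section describes a sham procedure, inert hand contact, matched session time, or a check of participants' expectation or belief about their group.

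**The concern.** A placebo comparison is meant to hold constant everything except the ingredient under test. Here the ingredient is the mobilization with movement. What the control arm lacks, however, is the whole treatment episode: the mobilization, plus whatever hands-on contact, practitioner time, guided movement and sense of being treated come with it. Randomization balances the women's characteristics at entry. It does not balance what is delivered afterwards, and blinding the outcome collector does not remove the participant's own expectation from a score that she reports herself.

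The stake is how a positive Aim 1 result would be read. Under the present wording it would be taken as a placebo-controlled effect of the technique. The section on future grant applications says that confirming the central hypothesis would warrant further investigation and makes a larger multi-site randomized trial the next step, so a misattributed effect could be carried into that trial's rationale and planning. No later analysis of these data could separate the components.

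**Working it through.** **Step 1: what differs between the arms.** From the Approach section:

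| Element | Treatment arm | Control arm |
|---|---|---|
| Standardized examination, including palpation | yes | yes |
| Baseline tasks | yes | yes |
| Mulligan evaluation | yes | yes |
| Mulligan treatment | yes | nothing described |
| Repeat of tasks, outcome measures and examination | yes | yes |

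Write the mean score as E (everything shared), plus M (mobilization), plus N (contact, time and expectation that accompany treatment beyond the shared part). The Aim 1 difference is

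(E + M + N) − E = M + N.

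The shared part cancels. The plan supplies no third quantity from which M could be separated from N.

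**Step 2: what is not stated.** The plan does not say whether the evaluation includes any trial mobilization. If it does not, the difference is M + N as above. If it does, and this delivers a fraction c of the mobilization effect to both arms, the contrast becomes (1 − c)M + N. The two departures act in opposite directions, and the documents do not show which applies.

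**Step 3: the plan's own figures.** The Statistical Analysis section gives 17 per group for 80% power at alpha 0.05, and 36 in total (18 per group) after 5% dropout. The dropout step reproduces: 17/0.95 = 17.9, so 18 per group; 34/0.95 = 35.8, so 36. The 17 itself cannot be checked, because no effect size, SD or sidedness is given. Solving backwards with a t-test gives a standardized difference of 0.99 (two-sided) or 0.87 (one-sided). The point does not rest on these figures.

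**Step 4: illustration of size.** The documents give no value for N, so the following is an assumption shown as a range. Set M = 0 and let N shift one score by d SD. The chance that a two-sided 5% two-sample t-test is significant comes from the noncentral t distribution with 2n − 2 degrees of freedom and noncentrality d√(n/2). With n = 17 per group, the critical value on 32 degrees of freedom is 2.04:

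| Assumed shift d | Noncentrality | Chance of significance |
|---|---|---|
| 0 | 0 | 5% |
| 0.1 | 0.29 | 5.9% |
| 0.2 | 0.58 | 8.7% |
| 0.3 | 0.87 | 13.6% |
| 0.5 | 1.46 | 29.3% |

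The Approach section recruits twenty women, a separate discrepancy. With 10 per group, the figures for d = 0.3 and 0.5 are 9.7% and 18.5%.

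These are not type I error rates for the contrast that is actually made; for M + N the test keeps its 5% level. They are the chances of a significant result that would be misread if it were credited to M.

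**The case against.** The strongest reply is that evaluation-only is a sound comparator. A control condition normally is the part that both arms share, and the effect of adding treatment to evaluation is a real clinical question. That stands, and it limits the point to the label and to what is concluded. It is also true that much contact is shared, so only the excess in the treated arm is unmatched. A woman new to the method might even take a hands-on evaluation for the intervention, which would make it a weak placebo. Nothing in the plan supports relying on that, and no check is planned.

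Three stronger readings are tempting and should not be made:

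- A reader might infer that women would recognise their group because they are "given an informational packet explaining the methods, risks, and benefits of participation". The contents of that packet are not given, so it is not known whether it describes each arm. That a control participant could work out her group is plausible but not established.
- A reader might infer that scores are taken within minutes of treatment, or that the treated session is longer by a known amount. The aim concerns immediate change, but no interval or session length is stated for either arm.
- A reader might infer that the whole trial is uninformative. The Aim 2 movement and muscle-activity measures depend less directly on self-report, and Aim 1 still estimates an add-on effect.

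Finally, the trial is described as exploratory. That lowers the severity. It does not make the placebo statement accurate.

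**Conclusion.** The point holds in this form: the described arms do not have the property the plan claims for them. As written, Aim 1 compares evaluation plus treatment with evaluation alone, and a difference in self-reported scores cannot be assigned to the mobilization. This follows from the arm descriptions and needs no numerical assumption.

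The size of the non-specific part is unknown. The range of about 6% to 29% at 17 per group assumes no mobilization effect, a shift of 0.1 to 0.5 SD and a single two-sided test. At the low end the consequence is slight. Given the exploratory purpose and a remedy that is mostly wording, this is a should-fix matter.

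**What to change.** 1. In the Approach and Statistical Analysis sections, rename the arm *evaluation-only control*. Remove the placebo and participant-blinding claims and the sentence on minimal confounding. State the Aim 1 conclusion as evaluation plus treatment versus evaluation alone, including effects of contact and expectation.
2. Reveal the allocation to the practitioner only after the shared evaluation has been completed and recorded, so that this part is identical in both arms. State whether the evaluation includes any trial mobilization. Because the practitioner must then learn the allocation in order to treat, the statement that the treating clinician is blind has to be brought into line.
3. After the final measures, ask each participant which group she believes she was in, and report the answers by arm.

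The cost is a less favourable claim, one concealment step at the visit and one question per participant. The question describes beliefs about allocation; it does not separate the mobilization from the non-specific effects.

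If the sponsor wishes to keep the placebo claim, the arm descriptions and the design statement must be reconciled. The content of any sham procedure is for the investigators to decide.
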